9.1 Study design

This study has a cohort design.

Cohorts of first-time users of either rivaroxaban or standard of care will be identified using the date of first dispensing (index date) of the respective drug (index drug).

A patient will be considered eligible to enter the study cohort as a first-time user of rivaroxaban or a first-time user of “standard of care” when he or she has a first dispensing of the drug recorded during the enrolment period. In the Netherlands, for VTE prevention, DVT/PE treatment and SPAF, standard of care is treatment with a vitamin K antagonist (acenocoumarol or phenprocoumon), and for the secondary prevention of ACS, standard of care is antiplatelet drug(s) such as low-dose acetylsalicylic acid, clopidogrel, dipyridamole, prasugrel, ticlopidine and ticagrelor.

Patients who qualify as members of both cohorts on the same day, will be excluded. First-time users who have any record of being prescribed the other study drug prior to the enrolment period can only join their index drug cohort; these will be categorized as non-naïve, see below (i.e. patients with a previous dispensing of rivaroxaban can only join the standard of care cohort and those with a past dispensing for standard of care can only join the rivaroxaban cohort).

Patients who are first-time users of both rivaroxaban and comparison study drugs during the enrolment period will be assigned to a cohort based on first dispensing, with the date of this dispensing being the index date.

Many patients with ACS have a history of ischaemic heart disease for which platelet inhibition is standard treatment, and thus exclusion of patients with prior use of platelet inhibitors risks excluding a majority of typical ACS patients. Therefore, in patients treated for ACS, those who have been using a vitamin K antagonist or another oral anticoagulant-before the index date will be excluded but those who have been using one or more platelet inhibitors will remain eligible to enter the study.

Standard of care for ACS patients is combination therapy, and as such cohort assignment will be based on first use of rivaroxaban (in combination with aspirin or clopidogrel, or multi-antiplatelet therapy), or use of aspirin and clopidogrel and/or other antiplatelet medications.

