9.2 Setting

Study drug users will be selected from the outpatient pharmacy database. This database records all outpatient dispensings from primary and secondary care in a well-defined geographic area. All study drug users living in this area will be captured in the database. All patients aged 2 years and above who have been registered in the database for at least 1 year before the index date will be included. A sub-population will be defined of patients for whom GP recorded information is also available.

The enrolment period will start on December 10, 2011 (the day after rivaroxaban received first marketing authorization in the Netherlands for the ‘treatment of DVT and long-term secondary prevention of recurrent DVT and PE’). End of enrolment will be 31 December 2017 and end of follow-up will be 31 December 2018. Interim reports will be provided for data collected 2 and 4 years after the date that rivaroxaban receives reimbursement approval for DVT treatment (see [Section 6](#) for detailed milestones). The characteristics of the two study cohorts in the first year and subsequent years of the enrolment period will be compared.

The drug utilization analysis ([Section 8.1.1](#)) will be performed in the sub-population captured by both the outpatient pharmacy database and the GP database, in order to enrich the data for the assignment of indication of use.

The Adverse Outcomes analysis (Sections [8.1.2](#) and [8.2](#)) will be performed in the full rivaroxaban cohort (outpatient pharmacy database with outcomes available from Medical Register), using the dosing as a proxy for the indication when this information is not available, and in the subcohort of comparator drug users captured by both the outpatient pharmacy database and the GP database.

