9.3.2 Safety and effectiveness outcomes

For each outcome, potential cases will be identified using ICD-9-CM diagnostic codes ([Annex 3](#)) from hospital discharge diagnosis records.

For the purpose of this study, clinically relevant bleedings will be defined as bleedings leading to hospital admission. This restriction is needed to minimize differential misclassification caused by the variability in patients' behavior in seeking care for less severe bleedings. Similarly, the physicians'

attitude towards recording these events may differ between new drugs and standard of care. The consequence of restricting to bleedings identified through hospitalization or referrals is that bleedings leading to death before contact with a health care professional or hospital admission will be ignored. It is assumed that the number of bleeding events missed due to this restriction is small. Nevertheless, the magnitude and impact of this restriction will be assessed in another study of this PASS program (Swedish Record-linkage study).

9.3.2.1 Occurrence of intracranial haemorrhage, gastrointestinal bleeding and urogenital bleeding: case definitions

Intracranial haemorrhage (Annex 3, Table 4)

Cases of intracranial haemorrhage will be identified in patients admitted to the hospital that meet the criteria for one of the three following categories:

- incident cases of intracerebral haemorrhage recorded following or in association with computed tomography, magnetic resonance imaging (MRI) or x-ray angiography, or an appropriate therapeutic procedure.
- incident cases of subarachnoid haemorrhage recorded following computed tomography, MRI, X-ray angiography or lumbar puncture, or an appropriate therapeutic procedure.
- incident cases of epidural, dural, subdural and arachnoid haemorrhage recorded following computed tomography, MRI, x-ray angiography or lumbar puncture, or an appropriate therapeutic procedure.

As therapeutic procedures are not captured in the database, potential cases will be identified by hospital discharge diagnoses (ICD-9-CM). PHARMO will apply for chart review on therapeutic procedures to define the case (see [Section 9.4](#)).

Gastrointestinal bleeding (Annex 3, Table 5)

A patient will have to meet the following criteria to be considered a case of gastrointestinal bleeding:

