9.3.2.2 Secondary safety outcome: case definition

Other bleeding leading to hospitalization (Annex 3, Table 7)

A patient will have to meet the following criteria to be considered a case of “other bleeding”:

- admitted to hospital with a bleeding event occurring before hospitalization (i.e. excluding in-hospital bleeding events).

Cases will be identified by hospital discharge diagnoses (ICD-9-CM).

Non-infective liver disease (Annex 3, Table 8)

A patient will have to meet both of the following criteria to be considered a case of non-infective liver disease:

- The patient having been admitted to hospital with acute liver injury.
- Free of cancer, other liver disease (including infectious hepatitis, chronic liver disease etc.), gallbladder or pancreatic disease and alcoholism.

Potential cases will be identified by hospital discharge diagnoses (ICD-9-CM) and chart review will be applied for (see [Section 9.4](#)) to define the case. If chart review is approved and laboratory values are available in the chart, the following additional criterion will be applied: an increase of more than three times the upper limit of the normal range in alanine aminotransferase (ALT) or aspartate aminotransferase (AST), or a combined increase in ALT, AST or alkaline phosphatase (AP) and total bilirubin, provided one of them is twice the upper limit of the respective normal range.

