9.4 Data sources

Data for the study will be obtained from a linked cohort created using the PHARMO Database Network. The PHARMO Database Network is a population-based network of healthcare databases and combines data from different healthcare settings in the Netherlands. These different data sources are linked on a patient level through validated algorithms. Detailed information on the methodology and the validation of the used record-linkage method can be found elsewhere ([van Herk-Sukel et al. 2010](#); [Herings RMC 2012](#))

The longitudinal nature of the PHARMO Database Network system enables follow-up of more than 4 million residents (25% of total population) of a well-defined population in the Netherlands for an average of ten years. Data collection period, catchment area and overlap between data sources differs. Therefore, the final cohort size for any study will depend on the data sources included. As data sources are linked on an annual basis, the average lag time of the data is 1 year. All electronic patient records in the PHARMO Database Network include information on age, sex, socio-economic status and mortality. Other information available is dependent on the data source

To address the objectives of the present study, the following data sources will be used: outpatient pharmacy database, Dutch National Medical Register, general practitioner (GP) data and inpatient pharmacy database. The outpatient pharmacy database has a source population of about 4 million residents and is fully linked to the national Dutch National Medical Register. The GP and inpatient pharmacy databases each represent different, partially overlapping subsets of the outpatient pharmacy/Medical Register source population.

The drug utilization analysis will be performed in the subpopulation captured by both the outpatient pharmacy database and the GP database, in order to enrich the data for the assignment of indication of use. The Adverse Outcomes analysis will be performed in the full rivaroxaban cohort (outpatient pharmacy database with outcomes available from Medical Register), using the dosing regimen as a proxy for the indication when this information is not available, and in the subcohort of comparator drug users captured by both the outpatient pharmacy database and the GP database.

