9.7.2.1 Sub-cohorts

The PHARMO Database Network consists of databases which differ in geographical catchment area. Data from GP records and inpatient dispensings are available for different sub-cohorts of the source population, which is based on the outpatient pharmacy dispensing database.

General practitioner data will be used as an additional source for identification of the indication of study drug use in the drug utilization analysis and to identify renal status in the safety analysis.

To determine the renal status of patients primary care information and hospital discharge diagnoses will be used. For the subset of patients with GP data, eGFR values (when available) allow classification of the GFR. In the total subset, ICD-9 hospital discharge diagnoses related to renal impairment will be used (Table 12):

In addition, use or non-use of medication used by patients with advanced renal disease is available. Patients will then be characterised as:

End-stage renal disease

- a code for dialysis (V45.1 or V56) given within one year before index date.

Advanced renal disease

- a diagnosis of chronic renal failure (585) given 3 years or more before index date or
- any diagnosis of renal disease (see list) before index in combination with use of phosphate binding drugs, sodium bicarbonate or erythropoietic drugs within one year before index date.
- not being categorized as end stage renal disease (see above)

Mild renal disease

- any diagnosis of renal disease (see ICD-9 list) before index
- not being categorized as end stage or advanced renal disease (see above)

No renal disease

- none of the above

Grouped by renal status, data will be analysed to determine:

- initial indication for rivaroxaban
- rivaroxaban dose received
- crude incidences (calculated as described above) of primary safety outcomes and outcomes related to effectiveness by renal function and by dose

Inpatient dispensing data will be used to follow patients from the date that rivaroxaban or standard of care is started in hospital. The occurrence of an intracranial haemorrhage, gastrointestinal bleeding or urogenital bleeding during hospitalization will be determined on the basis of discharge diagnoses and, if feasible, medical chart review.

It is likely that a potential misclassification of renal failure will be more pronounced in mild renal failure whereas severe forms of renal failure most likely will be readily identified.

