9.9 Limitations of the research methods

Limitations of this study include:

- The possibility for unmeasured confounders for bleeding affecting the data e.g. inadequate or missing recording of ethnicity, alcohol intake or over-the-counter use of some medications.
- Underreporting of events occurring in-hospital i.e. bleeding events occurring during admission for another diagnosis are not recorded as a primary diagnosis and recoding of secondary diagnoses are not mandatory.
- Prescriptions started in-hospital or events in the immediate post-discharge period may be missed from outpatient (pharmacy and general practitioner) records.
- Inadequate data concerning medication compliance.
- Potential for misclassification of exposure to vitamin K antagonist due to complex dosing with multiple strengths of tablet.
- For the effectiveness outcome of DVT/PE, it is possible that discharge diagnoses may lack sensitivity, and data may need to be interpreted with caution ([Severinsen et al. 2010](#)).

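### The in-hospital-start analysis mixes outpatient selection with follow-up from the inpatient start and cannot order bleeds within the starting admission, so its bleeding rate is unreliable

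*Protocol*

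**What the plan says.** All references are to the protocol.

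- **Selection.** Section 9.2: "Study drug users will be selected from the outpatient pharmacy database". Section 9.1 sets the index date at the first dispensing and does not say whether an inpatient dispensing counts.
- **Inpatient sub-cohort.** Section 9.7.2.1: "Data from GP records and inpatient dispensings are available for different sub-cohorts of the source population, which is based on the outpatient pharmacy dispensing database". It then states: "Inpatient dispensing data will be used to follow patients from the date that rivaroxaban or standard of care is started in hospital". The three primary bleeding types during that stay are to be found from discharge diagnoses, with chart review where feasible.
- **Recording of in-hospital bleeds.** Section 9.9 lists as a limitation that "bleeding events occurring during admission for another diagnosis are not recorded as a primary diagnosis and recoding of secondary diagnoses are not mandatory". It also says that treatment begun in hospital may be absent from outpatient records.
- **Main outcome.** Section 9.3.2: "clinically relevant bleedings will be defined as bleedings leading to hospital admission". Section 9.7.2 follows patients from the index date.
- **Chart review.** Sections 9.4 and 9.8 make it subject to approval by the national register and by each hospital. They describe it as further information on a case.

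**The concern.** Two features of the sub-cohort analysis do not fit together.

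The first is entry. If membership depends on an outpatient dispensing but the clock starts earlier, in hospital, then membership is decided by something that happens after follow-up begins. Patients who die of a bleed or stop because of one before any outpatient dispensing are left out. For those who stay in, the interval from the in-hospital start to the first outpatient dispensing is guaranteed free of such events.

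The second is ascertainment and order. A discharge diagnosis belongs to the whole admission and does not show whether the bleed came before or after the first dose. A patient admitted with a bleed and started on the drug later in the stay could be counted as having bled on treatment. A bleed that truly followed the start may never be coded.

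This is the only analysis that follows patients from an in-hospital start. The main analysis starts at the index date, and the sensitivity analyses in section 9.7.2.2 concern mode of action. If this analysis is unreliable, nothing else in the protocol covers bleeding in that period.

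**Working it through.** The plan gives no figure on this point. It states neither the share of in-hospital starts nor the completeness of secondary coding. The study-size figure in section 9.5 does not bear on it. The check is therefore mainly a reading of the sections against each other, followed by an illustration with assumed values.

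**Step 1: who enters.** Section 9.2 gives the only selection rule, which is outpatient dispensing. Section 9.7.2.1 places the inpatient data inside a source population based on outpatient dispensing. No section gives an inpatient route of entry. Applied to in-hospital starters:

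- Bleed before discharge, fatal or ending treatment, no outpatient dispensing: not selected, event lost.
- Bleed before discharge, treatment continued, later outpatient dispensing: selected, event countable if coded.
- No bleed, later outpatient dispensing: selected, in-hospital days added to person-time.

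**Step 2: what the codes can show.** By section 9.9, a bleed during an admission for another reason is not the primary diagnosis, and secondary coding is optional. It follows that:

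- A bleed after the in-hospital start can appear only in the optional secondary field.
- A bleed in the principal field is normally the reason for admission, so it precedes the start.

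The better-recorded field therefore mostly holds bleeds of the wrong order, and the field that could hold bleeds of the right order is incomplete. Chart review could settle the order for coded cases. As described, it would probably not recover uncoded ones.

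**Step 3: illustration (all values assumed).** Let

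- q = share of patients with an in-hospital bleed after the start who later receive an outpatient dispensing,
- s = share of such bleeds that are coded,
- m = number of pre-start bleeds wrongly counted, per true post-start bleed.

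With q and s independent, counted events / true events = q × s + m.

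| Reading of entry | q | s | q × s |
|---|---|---|---|
| Outpatient dispensing required | 0.5 | 0.5 | 0.25 |
| Outpatient dispensing required | 0.7 | 0.7 | 0.49 |
| Outpatient dispensing required | 0.9 | 0.9 | 0.81 |
| Not required | 1 | 0.5 to 0.9 | 0.50 to 0.90 |

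With m = 0, the count is 25% to 81% of the truth if an outpatient dispensing is required, and 50% to 90% if not. The sign reverses once m exceeds 1 − q × s: above 1 − 0.25 = 0.75 at the lower end, and above 1 − 0.81 = 0.19 at the upper end. Nothing in the documents fixes m, so the net direction is open. These are shares of events, not of rates.

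**Step 4: the comparison between cohorts.** With a true rate ratio of 1 and m = 0, the observed ratio is the ratio of capture in the two cohorts. Equal capture (0.7 / 0.7) gives 1.0, 0.5 / 0.7 gives 0.71, and 0.7 / 0.5 gives 1.40. The documents do not say whether capture differs.

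**The case against.** The strongest reply is that the entry rule is inferred. No section says that an in-hospital starter needs a later outpatient dispensing. Section 9.1 speaks only of a first dispensing. Section 9.4 says "The outpatient pharmacy database has a source population of about 4 million residents and is fully linked to the national Dutch National Medical Register", so the source population may mean residents of the catchment area rather than outpatient drug users. On that reading, entry is at the in-hospital start and the guaranteed-time argument falls away. Detail of cohort entry may also sit in a statistical analysis plan that is not shown.

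This stands in part. The outpatient requirement is a strong inference, not a stated rule. But the protocol itself fixes both a selection source and a start of follow-up, and applied as written the two conflict. The ordering problem remains under either reading.

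A second reply is that section 9.9 already discloses under-recording. It does. However, section 9.7.2.1 then relies on the same codes with no rule for bleeds in the starting admission, and chart review is conditional.

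A reader might also infer a clash with section 9.3.2.2, where the case definition is limited by "excluding in-hospital bleeding events". That wording applies only to the secondary outcome of other bleeding. The inpatient analysis covers the three primary bleeding types, so there is no contradiction. Nor does the protocol single out bleeding in the first days of treatment as a specific risk; section 7 names haemorrhage in general.

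**Conclusion.** The point holds as a defect of a supporting analysis on the primary safety outcomes. On the most natural reading, selection removes early fatal or treatment-ending bleeds and leaves guaranteed time. On any reading, discharge codes cannot separate bleeds before the start from bleeds after it. The in-hospital bleeding rate cannot be relied on.

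A reader might infer that early bleeding is certainly understated. The documents do not support that: selection and under-coding pull the rate down, mis-ordered bleeds push it up, and neither can be sized. A reader might also infer that the comparison of rivaroxaban with standard of care is biased. That requires capture to differ between the cohorts, which is unknown. The 25% to 81% range rests wholly on assumed values of 0.5 to 0.9 for q and s, with no mis-ordered events.

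**What to change.** Change section 9.7.2.1 as follows.

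1. For the inpatient sub-cohort, define entry as the first inpatient or outpatient dispensing, whichever is earlier, and state that no later outpatient dispensing is required.
2. Do not count a bleed that is the principal diagnosis of the starting admission as an event after the start, unless chart review shows that it followed the first dose.
3. State whether chart review covers all in-hospital starters or only coded cases.
4. Report the in-hospital rate separately from the rates of bleeding leading to admission (sections 9.3.2 and 9.7.2), labelled as probably under-ascertained. With rule 2 in place, most of the upward error is removed and under-coding is the main error left.

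Leave the case definition of the main analysis unchanged. Restricting it to principal diagnoses would alter the primary outcome for the sake of a sub-cohort problem.

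The cost is protocol wording and some re-selection in inpatient data that are already planned for use. The price is a caveated estimate that still depends on optional secondary codes.

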- the specific site of bleeding originating in the upper or lower gastrointestinal tract or, more specifically, in the oesophagus, stomach, duodenum, jejunum, ileum, colon or rectum.
- for upper gastrointestinal bleeding, the lesion type being erosion, gastritis, duodenitis or peptic (gastric or duodenal) ulcer.
- the lesion type being NOT related to cancer.

Cases will be identified by hospital discharge diagnoses (ICD-9-CM).

Urogenital bleeding (Annex 3, Table 6)

A patient will have to be admitted to the hospital for urogenital bleeding, i.e. the specific site of bleeding originating in the urogenital tract.

Cases will be identified by hospital discharge diagnoses (ICD-9-CM).

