9.7.2 Safety and effectiveness outcomes

The two cohorts (of first-time users of rivaroxaban and first-time users of standard of care) will be followed up from the index date until 12 months after the end of the enrolment period for potential outcomes (safety and effectiveness). For each outcome, the first hospitalization for that outcome during the follow-up period will be identified. A separate follow-up will be performed for each of the outcomes.

For all outcomes (for DVT/PE treatment, SPAF and ACS), crude incidence rates will be estimated in both cohorts, using an as-treated approach. In this, person–time will be categorized into current, recent, past and non use. Current use will refer to person–time up to 7 days after the end of supply of the index drug, recent use will refer to person–time up to 90 days after the end of current use, past use will include all person–time contribution after the end of recent use up to 1 year after the end of current use, non-use will include all remaining time person–time contribution after past-use until end of follow-up.

Age- and sex-adjusted rate ratios with 95% CIs will be estimated for each of the three adverse outcomes comparing rivaroxaban with standard of care using Poisson regression analysis. Where numbers and data permit, adjustment will be made for relevant co-medication (described in the drug utilization section), indication and previous hospitalization for bleeding.

As a general strategy, no data imputation strategies will be applied to supplement missing data. The requirement for inclusion is complete data for critical variables such as exposure to rivaroxaban or standard of care and hospitalizations for bleedings or any other outcome event; otherwise this individual is not eligible to be a member of the study population. However, missing values may occur for potential confounder or effect modifying variables. In this case, individuals with missing values will be kept in the analysis and a separate category will be created for missing values of that variable. In sub-analyses to evaluate confounding or effect modification by variables with a large proportion of missing values, the evaluation will be considered to be conducted on the subset with complete data for the variable of interest.

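### In the inpatient-dispensing sub-cohort, a primary bleed that preceded the in-hospital drug start can be counted as an on-treatment event, because discharge codes do not show when the bleed began

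*Protocol*

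**What the plan says.** Section 9.3.2 of the Protocol sets a general rule: "clinically relevant bleedings will be defined as bleedings leading to hospital admission". The urogenital definition repeats it ("A patient will have to be admitted to the hospital for urogenital bleeding"), and section 9.7.2 counts events to match: "the first hospitalization for that outcome during the follow-up period will be identified". For finding cases, section 9.3.2 says that "potential cases will be identified using ICD-9-CM diagnostic codes", taken from hospital discharge records. It does not say whether the code must be the main diagnosis.

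Only one outcome carries an explicit exclusion of bleeds that arise in hospital. This is the secondary outcome of other bleeding in section 9.3.2.2, where the patient must be "admitted to hospital with a bleeding event occurring before hospitalization (i.e. excluding in-hospital bleeding events". The gastrointestinal criteria cover site, lesion type and cancer ("the lesion type being NOT related to cancer") and are silent on timing.

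Section 9.7.2.1 adds an analysis in the subset with inpatient dispensing data. Follow-up there begins on the day the drug is started in hospital. For these patients, "The occurrence of an intracranial haemorrhage, gastrointestinal bleeding or urogenital bleeding during hospitalization will be determined on the basis of discharge diagnoses", with medical chart review added where feasible. Sections 9.4 and 9.8 make chart review subject to approval by the database provider and by each hospital.

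Section 9.9 lists as a limitation that "bleeding events occurring during admission for another diagnosis are not recorded as a primary diagnosis and recoding of secondary diagnoses are not mandatory".

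**The concern.** When the drug is started during an admission, the order of bleed and first dose within that admission decides whether the bleed belongs to exposed time. A discharge code says that a bleed was diagnosed in the admission, not on which day. Without a dating rule, a bleed that was the reason for admission can be counted against a drug that the patient had not yet received.

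The events concerned are the three primary safety outcomes. In this sub-cohort they are also collected under a different definition from the rest of the study: bleeds in hospital rather than bleeds that lead to admission. The Protocol does not say whether these events stay in a separate table or join the rate ratios of section 9.7.2.

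**Working it through.** The Protocol gives no figure for this point, so the main check is to set its statements side by side.

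**Step 1. What a code can show.** Section 9.9 says that bleeds arising during an admission for something else are not recorded as the primary diagnosis, and that secondary diagnoses need not be recorded. It follows that a bleed coded as the primary diagnosis was normally the reason for admission.

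**Step 2. Apply this to the admission in which the drug is started** (section 9.7.2.1, discharge diagnoses only, no chart):

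| Sequence | Where the bleed is coded | Found from codes? | On treatment? |
|---|---|---|---|
| Admitted for the bleed, drug started later | Normally primary | Yes | No |
| Admitted for another reason, bleed, then drug started | Secondary, optional | Only if coded | No |
| Admitted for another reason, drug started, then bleed | Secondary, optional | Only if coded | Yes |

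The sequence found most reliably is off treatment. The only on-treatment sequence depends on an optional code and cannot be told apart from the second row.

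**Step 3. Look for another source of onset.** Sections 9.3.2, 9.7.2, 9.7.2.1, 9.8 and 9.9 give none except chart review, which is conditional. No fallback is stated for when approval is refused.

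**Step 4. Compare the definitions.** Section 9.3.2 requires the bleed to lead to admission. Section 9.7.2.1 takes bleeds during hospitalization. The exclusion that would separate the two is written only in section 9.3.2.2, for other bleeding.

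**Step 5. Size.** The share of wrongly counted events is not given. Two illustrations, both on assumed shares, show what would happen in an analysis that includes such events.

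- *Same absolute rate of wrong events in both cohorts.* Let f be their share of counted comparator events. Observed ratio = (1 − f) × true ratio + f. With a true ratio of 1.5:
  - f = 0.05 gives 0.95 × 1.5 + 0.05 = 1.475
  - f = 0.30 gives 0.70 × 1.5 + 0.30 = 1.35
- *Different shares by cohort.* With shares f1 (rivaroxaban) and f0 (comparator), observed ratio = true ratio × (1 − f0)/(1 − f1). With a true ratio of 1.0:
  - f1 = 0, f0 = 0.20 gives 0.80
  - f1 = 0.20, f0 = 0 gives 1/0.80 = 1.25

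The ratio can move either way.

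**The plan's own figure.** The study size in section 9.5 does not bear on this point, but it reproduces. Expected events are 12,000 × 0.005 = 60 and 48,000 × 0.005 = 240. The standard error is √(1/60 + 1/240) = 0.1443. Assuming two-sided 5% and a true ratio of 1, power is Φ(ln 1.5/0.1443 − 1.96) = 0.802, against the stated 80%.

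**The case against.** The strongest reply is that the main analysis is already sound. It selects users from outpatient dispensings, starts at first dispensing, requires the bleed to lead to admission, and counts the first hospitalization for the outcome. Discharge codes only find potential cases, and the code position that implements the rule could be settled in an analysis plan. This stands. A reader might infer that in-hospital bleeds are counted throughout the study because no diagnosis position is stated. The documents do not support that: the general rule of section 9.3.2 covers all bleeds, and section 9.9 expects in-hospital bleeds to be under-recorded, not over-counted.

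A second reply is that section 9.7.2.1 is a supplementary analysis meant to capture in-hospital starts and bleeds, so departing from the admission-based definition is its purpose. It starts follow-up at the first in-hospital use, which shows the intent to count later events, and chart review could settle timing where approved. The intent is clear, and the wording should be that earlier bleeds can be counted, not that they always are. But intent does not order events within one admission, and nothing is provided for when charts cannot be had.

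A third reply is that dropping every coded bleed of the initiating admission unless a chart confirms it could leave the sub-analysis nearly empty. That is fair, and the fix is narrowed for this reason.

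**Conclusion.** The point holds for the inpatient-dispensing sub-cohort. As written, section 9.7.2.1 allows a bleed that caused the admission to be counted in exposed person-time, while a true bleed after the drug start may go unrecorded. It also uses a definition of the primary bleeds that section 9.3.2 does not share, without saying how the two relate.

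This rests on reading section 9.7.2.1 as including the admission in which the drug is started, and on the account of coding in section 9.9. How often a study drug is started in an admission that was itself for a bleed is not stated, and it may be rare. The ratios of 1.35 to 1.475 and of 0.80 or 1.25 illustrate mechanism only; no percentage error for this study can be derived.

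Nor should a reader infer that the plan labels these bleeds as drug-related. It makes no causality judgement; section 9.7.2 only assigns events to current, recent, past or non-use time. The missing code position would be a weak point alone. It matters because sections 9.3.2, 9.3.2.2, 9.7.2.1 and 9.9 do not fit together.

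**What to change.** In section 9.7.2.1:

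- Do not count a bleed coded as the main diagnosis of the admission in which the drug was started, unless a chart confirms onset after the first dose.
- Report secondary-position bleeds of that admission separately, as in-hospital events of uncertain timing, and keep them out of the main rate ratios. This preserves the in-hospital description without depending on chart approval.

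In section 9.3.2:

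- State that the three primary bleeds, like other bleeding, exclude in-hospital events and are counted from the main discharge diagnosis of an admission that starts after the index date.
- Add any-position codes as a sensitivity analysis.

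The cost is a few sentences, one further analysis run and one separate table, with no new data. The downside is somewhat fewer events and lower sensitivity for in-hospital bleeds, which section 9.9 already describes as under-recorded.
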